8.3.5 ADVERSE EVENT REPORTING

All AEs (including SAEs) will be recorded in the eCRF database within the timelines outlined in the eCRF completion guideline.

Information to be collected includes event description, time of onset, clinician's assessment of severity, relationship to study product (assessed only by those with the training and authority to make a diagnosis), and time of resolution/stabilization of the event. All AEs occurring while on study must be documented appropriately regardless of relationship. All AEs will be followed to adequate resolution.

Changes in the severity of an AE will be documented to allow an assessment of the duration of the event at each level of severity to be performed. AEs characterized as intermittent require documentation of onset and duration of each episode.

8.3.6 SERIOUS ADVERSE EVENT REPORTING

The study clinician will immediately (within 24 hours of identification by the site) report to the Sponsor any SAE, whether or not considered study intervention related, including those listed in the protocol or Investigator's Brochure. The SAE Report must include an assessment of whether there is a reasonable possibility that the study intervention caused the event.

To report a Safety Event, please contact the main Safety Management phone/fax/email (or via the applicable country-specific toll-free numbers located in your study binder).

For fatal or life-threatening events, copies of hospital case reports, autopsy reports, and other documents are also to be submitted by e-mail or fax when requested and applicable. Transmission of such documents should occur without personal subject identification, maintaining the traceability of a document to the subject identifiers.

Additional information may be requested to ensure the timely completion of accurate safety reports.

Any medications necessary for treatment of the SAE must be recorded onto the concomitant medication section of the subject's eCRF and the event description section of the SAE form.

8.3.7 REPORTING EVENTS TO PARTICIPANTS

Not applicable.

8.3.8 SPECIAL SITUATIONS REPORTS

Special situation reports include all reports of medication error, abuse, misuse, overdose, reports of AEs associated with product complaints, and pregnancy reports regardless of an associated AE. Reports of adverse reactions in infants following exposure from breastfeeding, and reports of adverse reactions associated with product complaints and reports arising from occupational exposure are also considered special situation reports.

- A pregnancy report is used to report any pregnancy in female partners of male subjects on study
- Medication error is any unintentional error in the prescribing, dispensing, or administration of a medicinal product while in the control of the health care provider, subject, or consumer
- Abuse is defined as persistent or sporadic intentional excessive use of a medicinal product by a subject
- Misuse is defined as any intentional or inappropriate use of a medicinal product that is not in accordance with the protocol instructions or the local prescribing information
- An overdose is defined as an accidental or intentional administration of a quantity of a medicinal product given per administration or cumulatively which is above the maximum recommended dose as per protocol or in the product labelling (as it applies to the daily dose of the subject in question). In cases of a discrepancy in drug accountability, overdose will be established only when it is clear that the subject has taken the excess dose(s). Overdose cannot be established when the subject cannot account for the discrepancy except in cases in which the investigator has reason to suspect that the subject has taken the additional dose(s)
- Product complaint is defined as complaints arising from potential deviations in the manufacture, packaging, or distribution of the medicinal product

All special situation reports must be reported on the special situations report form and forwarded to Sponsor within 24 hours of the investigator becoming aware of the situation. These reports must consist of situations that involve study drug, but do not apply to non-Sponsor concomitant medications. Cases of overdose should also be reported on an SAE form within 24 hours of the Investigator becoming aware of the situation.

Special situations involving non-Sponsor concomitant medications do not need to be reported on the special situations report form; however, for special situations that result in AEs due to a non-Sponsor concomitant medication, the AE should be reported on the AE form.

Any inappropriate use of concomitant medications prohibited by this protocol should be appropriately documented as a protocol deviation.

Refer to the eCRF completion guidelines for full instructions on the mechanism of special situations reporting.

All clinical sequelae in relation to these special situation reports will be reported as AEs or SAEs at the same time using the AE eCRF and/or the SAE report form. Details of the symptoms and signs, clinical management, and outcome will be reported, when available.

8.3.9 REPORTING OF PREGNANCY

Pregnancies of subjects exposed to ZN-c5 must be reported and relevant information should be submitted to Sponsor using the pregnancy and pregnancy outcome forms within 24 hours. Monitoring should continue until the conclusion of the pregnancy. If the end of the pregnancy occurs after the study has been completed, the outcome should be reported directly to Sponsor.

To report a pregnancy, please contact the main Safety Management phone/fax/email (or via the applicable country-specific toll-free numbers) located in your study binder.

Refer to Section 10.4.5 for Contraceptive Requirements and Maternal and Paternal Exposure.

8.4 DOSE-LIMITING TOXICITIES AND TOXICITY MANAGEMENT

8.4.1 DEFINITION OF DOSE-LIMITING TOXICITY MONOTHERAPY DOSE ESCALATION

A dose-limiting toxicity (DLT) is a toxicity as defined below, excluding toxicities clearly related to disease progression or intercurrent illness, which occurs during the DLT evaluation period (Cycle 1) in each cohort:

- Grade ≥ 3 hematologic toxicity present for more than 7 days
- Grade ≥ 3 neutropenia (ANC < 1000/mm³) with fever (a single temperature of > 38.3°C or a sustained temperature of ≥ 38°C for more than one hour)
- Grade 3 thrombocytopenia with bleeding
- Grade ≥ 3 or higher non-hematologic toxicity, except:
 - Grade 3 nausea or emesis with maximum duration of 48 hours on adequate medical therapy
 - Grade 3 diarrhea which persists for < 72 hours in the absence of maximal medical therapy
- Grade ≥ 2 non-hematologic treatment-emergent adverse event (TEAE) that in the opinion of the
 investigator is of potential clinical significance such that further dose escalation would expose
 subjects to unacceptable risk
- Treatment interruption of ≥ 4 days due to drug-related toxicity
- Liver enzyme and bilirubin abnormalities meeting Hy's Law criteria (See Section 10.4.7)
- Any death not clearly due to the underlying disease or extraneous cause

For certain toxicities, such as laboratory assessments without a clear clinical correlate, a discussion between the investigator and Medical Monitor may take place to determine if this adverse event (AE) should be assessed as a DLT necessitating dose reduction. In addition, any toxicity which occurs during the DLT evaluation period meeting the protocol-defined stopping criteria (Section 7.1) will be considered a DLT.

During the DLT evaluation period (Cycle 1), subjects not completing at least 24 days of scheduled daily dosing of ZN-c5 for reasons other than drug-related toxicity (e.g., withdrawal of consent, rapid disease progression, etc.) may be replaced based on the discretion of the Safety Review Committee.

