8.4.2 DEFINITION OF DOSE-LIMITING TOXICITY – COMBINATION DOSE ESCALATION

A DLT is a toxicity as defined below, excluding toxicities clearly related to disease progression or intercurrent illness, which occurs during the DLT evaluation period (Cycle 1) in each cohort:

- Hematologic:
 - o Grade 4 neutropenia
 - Febrile neutropenia (defined as neutropenia Grade ≥ 3 [ANC < 1000 cells/mm³] and a body temperature ≥ 38.5°C) requiring antibiotic or antifungal treatment
 - o Any Grade 4 thrombocytopenia (< 25,000/mm³ or <25.0 x 109/L)
- Nonhematologic:
 - o Grade ≥ 3 toxicities despite adequate treatment (e.g., nausea, vomiting, diarrhea)
- Other:
 - o Any palbociclib treatment delay of greater than 7 days to start Cycle 2

Subjects who do not receive at least 24/28 doses of ZN-c5 and/or at least 85% of palbociclib doses in Cycle 1 for reasons other than DLT will be replaced.

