8.4.3.3 DOSE ADJUSTMENT OF ZN-C5

ZN-c5 will be held for any ZN-c5 related Grade ≥ 3 adverse event or any DLT.

ZN-c5 dosing may be restarted if the AE that resulted in the dose hold resolves to \leq Grade 1 (or baseline) within 21 days. If the toxicity does not resolve to \leq Grade 1 or baseline within 21 days, ZN-c5 will be permanently discontinued, unless deemed in the best interest of the patient to continue and after discussion between the Investigator and the Sponsor's Medical Monitor (Section 7.2).

Dose holds for reasons other than toxicity (e.g., scheduled surgery) are allowed for up to 21 days. Dose holds for reasons other than toxicity that last more than 21 days require that the subject be removed from study unless deemed in the best interest of the patient to continue and after discussion between the Investigator and the Sponsor's Medical Monitor (Section 7.2).

Doses withheld during a cycle will not be made up. When a dose reduction is required because of AEs/DLTs, no dose re-escalation will be permitted for the duration of study treatment unless mutually agreed upon by the Investigator and Sponsor.

For dose modifications based on the occurrence of ZN-c5 related AEs, see Table 9. Up to 2 dose reductions are allowed.

Table 9: Dose Reduction Criteria ZN-c5: All Phases

Dose Reduction Criteria	Dose Adjustment
Grade 4 (< 0.5 × 10 ⁹ /L) neutropenia lasting ≥ 8 days	
Febrile neutropenia requiring antibiotics	Reduce 1 dose level or discontinue treatment if
Grade 4 (< 25×10^9 /L) thrombocytopenia or Grade 3 (≥ 25 to < 50×10^9 /L) thrombocytopenia associated with Grade ≥ 3 bleeding and/or requiring platelet transfusions	occurring at the lowest dose level possible (which is 50 mg/day in the Dose Escalation Cohorts or Dose Level -2 in the Monotherapy Expansion/Phase 2 and Combination Phase 2) ^b
Any non-hematologic Grade 3 toxicity a, c	
Any non-hematologic Grade 4 toxicity ^c	Discontinue treatment ^b

- ^a Grade 3 nausea, vomiting, diarrhea, or constipation for < 48 hours do not require a dose reduction.
- If it is in the best interest of the subject to continue treatment in the opinion of the Investigator and after discussion with the Sponsor, the subject can continue treatment at a (further) reduced dose level.
- Includes laboratory values deemed clinically significant by the Investigator

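### The monotherapy DLT item for thrombocytopenia with bleeding says Grade 3 where it should say Grade ≥ 3, leaving a very narrow gap for Grade 4

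*Protocol*

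**What the plan says.** Protocol 8.4.1 defines monotherapy DLTs during Cycle 1, "excluding toxicities clearly related to disease progression or intercurrent illness". The haematologic items are "Grade ≥ 3 hematologic toxicity present for more than 7 days", neutropenia of Grade ≥ 3 with fever, and "Grade 3 thrombocytopenia with bleeding". Other items cover non-haematologic toxicity of Grade ≥ 3 (with exceptions for short-lived gastrointestinal events), Grade ≥ 2 non-haematologic events that the investigator considers too risky for further escalation, and "Treatment interruption of ≥ 4 days due to drug-related toxicity".

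Two further clauses in 8.4.1 involve judgement. The investigator and Medical Monitor may discuss whether certain toxicities should count as DLTs. A Cycle 1 toxicity that meets the protocol's stopping criteria, cited as Section 7.1, does count.

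Elsewhere the protocol ranks Grade 4 platelets above Grade 3. For the combination, 8.4.2 lists "Any Grade 4 thrombocytopenia" with no bleeding or duration condition. Table 9 in 8.4.3.3 reduces the ZN-c5 dose for Grade 4 alone, but for Grade 3 only where there is "thrombocytopenia associated with Grade ≥ 3 bleeding and/or requiring platelet transfusions".

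**The concern.** Within one list, the more severe platelet event can rank below the milder one. Platelets of 25 to below 50 ×10⁹/L with Grade 1 bleeding are a DLT at once. Platelets below 25 with the same bleeding must qualify through some other item. Since 8.4.2 and Table 9 both treat Grade 4 as worse, this reads as a drafting slip, not a decision.

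DLT counts drive Table 2 in Protocol 6.1.3 and so the MTD. They also govern when expansion accrual moves to a higher dose (6.1.6) and which ZN-c5 doses are open to combination escalation (6.1.5). An unlisted event would push towards escalation.

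**Working it through.** The plan states no figure for this point. The check tests a Grade 4 platelet event with bleeding against each DLT item and then sizes what is left.

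**1. Grades.** SAP Appendix 1, 11.2 sets Grade 3 at 25 to below 50 ×10⁹/L and Grade 4 at below 25. The bands do not overlap. Protocol 8.3.3.1 reports each episode at its worst grade, so an episode that falls below 25 is reported as Grade 4.

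**2. Item by item.**

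| Grade 4 platelets with bleeding in Cycle 1, and: | Listed DLT in 8.4.1? |
|---|---|
| Grade ≥ 3 for more than 7 days | Yes |
| the bleed is itself Grade ≥ 3 | Yes, non-haematologic item |
| drug-related interruption of 4 days or more | Yes |
| bleeding also present while platelets are 25 to below 50 | Arguably yes: 8.3.5 records severity changes "to allow an assessment of the duration of the event at each level of severity to be performed" |
| Grade 2 bleed | Only if the investigator elevates it |
| none of these | No; only through the two judgement clauses |

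**3. Main route: a short hold.** Section 8.4.3.3 requires ZN-c5 to be held for related Grade ≥ 3 events. The restart rule, "ZN-c5 dosing may be restarted if the AE that resulted in the dose hold resolves to" Grade 1 or lower (or baseline), allows 21 days and sets no minimum hold. Grade 1 starts at 75 ×10⁹/L. Eligibility (5.1, item 15a) requires at least 100, so the baseline alternative will not normally lower the target. Platelets must therefore rise by more than 75 − 25 = 50 ×10⁹/L within 3 days, because a fourth day meets the interruption item.

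**4. Blood-count schedule.** On-treatment haematology in Cycle 1 is scheduled for Days 8 and 15, then Cycle 2 Day 1. On nominal days, a Day 8 event is not re-sampled until Day 15, a hold of 15 − 8 = 7 days, which is already a DLT. A hold of 3 days or less therefore needs, in practice, unscheduled samples. Protocol 8.2.1.6 allows these.

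**5. Dose level.** At 50 mg/day, Table 9 calls for discontinuation on Grade 4 thrombocytopenia unless continuation is agreed with the Sponsor. That in effect meets the interruption item, so the main route lies essentially above 50 mg/day.

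**6. Evaluability.** With 3 hold days and no other missed dose, 28 − 3 = 25 doses are taken; 25/28 = 89.3%. The threshold in SAP 5.4 is 24/28 = 85.7%. The subject stays evaluable and, unless judgement intervenes, counts as having no DLT.

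**7. Possible second route: late onset.** If only days up to Day 28 count, an event starting on Day d leaves 28 − d + 1 hold days: 4 from Day 25, 3 from Day 26, 1 from Day 28. Onset on Days 26 to 28 could then miss the interruption item. The text does not say whether later days count. Detection would normally need an unscheduled sample or an early Cycle 2 Day 1 draw.

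**8. Effect on Table 2.** One unlisted event leaves 0 of 3 (escalate) instead of 1 of 3 (enrol 3 more), or 1 of 6 (escalate) instead of 2 of 6 (do not escalate).

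**The case against.** The strongest reply is that the omission has almost no practical reach. Bleeding must stay below Grade 3 and be confined to the time platelets are below 25, and recovery must be fast and documented by extra samples. The ZN-c5 risks in Protocol 2.3.1 are sex-organ effects, hepatic injury and reduced erythropoiesis; thrombocytopenia is not among them. A Safety Review Committee would probably read Grade 3 as a floor. All of this stands, and it limits the point to a minor one.

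The two judgement clauses also matter. They mean a subject in the gap does not automatically count as free of DLT. They do not close the gap. The Medical Monitor discussion is optional, and its example is laboratory findings with no clinical counterpart, whereas bleeding is one. The stopping-criteria clause cites 7.1, which lists none; the list is in 7.2, where the entry for unacceptable toxicity is undefined. A Table 9 dose reduction is not itself a DLT criterion.

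A reader might infer a further route through short events not attributed to ZN-c5. Section 8.3.3.2 leaves almost nothing there. Attribution is yes or no, and a no requires evidence of another cause. Events clearly due to progression or intercurrent illness are excluded from the DLT definition anyway. What remains is mainly causes such as a concomitant medication, and leaving those out is hardly a safety defect.

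**Conclusion.** The wording is wrong as it stands: the item should cover Grade 3 and above. Confidence in that is high, because the neighbouring items, 8.4.2 and Table 9 all point the same way and no other text fully closes the gap.

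The practical size is very small. What remains is chiefly a related event above 50 mg/day with a documented hold of 3 days or less, and possibly a Day 26 to 28 onset under a counting rule the protocol does not state. Both assume bleeding below Grade 3, confined to the Grade 4 phase, and not elevated by judgement.

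It would be tempting to conclude that DLTs were under-counted or that the MTD was set too high. The documents do not support that. They report no such event and give no thrombocytopenia rate, so no probability can be attached. Severity: minor.

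**What to change.** Insert the ≥ sign, so that the item covers thrombocytopenia of Grade 3 or higher with bleeding. This costs one symbol and helps wherever the text is used again.

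For this trial, SAP Section 8 records a data cut-off of 18 May 2022, set after the primary objectives were met, so the useful step is a cross-read of outputs already planned. These are the haematology shift table to worst Cycle 1 value (SAP 6.6.4) and the AE and DLT listings (SAP 6.6.3). Unscheduled values are eligible for worst-case analyses (SAP 6.6.1), so a short nadir that was measured should appear.

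If no monotherapy-escalation subject had Grade 4 platelets, the question is closed. If one did, check whether that subject also bled and was not scored as a DLT. This covers about 36 planned subjects and needs no new data or analysis.

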8.4.2 DEFINITION OF DOSE-LIMITING TOXICITY – COMBINATION DOSE ESCALATION

A DLT is a toxicity as defined below, excluding toxicities clearly related to disease progression or intercurrent illness, which occurs during the DLT evaluation period (Cycle 1) in each cohort:

- Hematologic:
 - o Grade 4 neutropenia
 - Febrile neutropenia (defined as neutropenia Grade ≥ 3 [ANC < 1000 cells/mm³] and a body temperature ≥ 38.5°C) requiring antibiotic or antifungal treatment
 - o Any Grade 4 thrombocytopenia (< 25,000/mm³ or <25.0 x 109/L)
- Nonhematologic:
 - o Grade ≥ 3 toxicities despite adequate treatment (e.g., nausea, vomiting, diarrhea)
- Other:
 - o Any palbociclib treatment delay of greater than 7 days to start Cycle 2

Subjects who do not receive at least 24/28 doses of ZN-c5 and/or at least 85% of palbociclib doses in Cycle 1 for reasons other than DLT will be replaced.

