6.1.3 DEFINITION OF MTD AND RP2D

During both the Monotherapy and Combination Dose Escalation cohorts of the study, dose limiting toxicity (DLT) will be assessed during Cycle 1. A cohort will be expanded from 3 to 6 subjects if one of the initial 3 subjects demonstrates DLT. Cohort expansion or dose escalation will follow the rules outlined in Table 2. Subjects who do not receive at least 24/28 doses of ZN-c5 or at least 18/21 doses of palbociclib in Cycle 1 for reasons other than DLT will be replaced.

Table 2: Dose Escalation Rules

If DLT was observed in:	Then:
0 in 3 subjects	Proceed with enrollment in next cohort
1 of 3 subjects	Enroll 3 additional subjects in current cohort
1 of 6 subjects	Proceed with enrollment in next cohort
≥ 2 subjects in a cohort	Do not escalate; enroll 3 additional subjects in previous
	cohort or new intermediate dose level

The MTD is defined as the highest dose level with ≤ 1 DLT in a cohort of 6 subjects. The RP2D may be lower but will not be higher than the MTD. The MTD/RP2D for monotherapy treatment may be different than the MTD/RP2D for combination therapy.

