6.1.5 COMBINATION DOSE ESCALATION

Dose escalation in combination with palbociclib will be initiated at a ZN-c5 dose that is deemed well-tolerated in the Monotherapy Dose Escalation and will proceed with higher ZN-c5 doses, as tolerated in the Monotherapy Dose Escalation, based on standard rules of 3+3 design in order to define an MTD/RP2D for ZN-c5 in combination with palbociclib (Section 6.1.3). The total number of patients will depend upon the number of dose escalations necessary, but it is estimated to be approximately 40 subjects (including alternate dosing schedules, e.g., BID, and possible backfill).

Dose levels and schedule will follow the dose levels and schedule per the Monotherapy Dose Escalation.

Additional subjects can be enrolled at a lower dose level already deemed tolerated (backfill). At least 6 subjects will be treated at the MTD/RP2D.

The subjects treated in the Combination Dose Escalation can possibly count towards the futility assessment stage accrual (Section 9.2.4, Combination Phase 2).

The dose of palbociclib used in the combination phases of the study will be the Regulatory Authority approved dose and schedule (125 mg PO QD \times 21 days, followed by 7 days off treatment).

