7.2 PARTICIPANT DISCONTINUATION/WITHDRAWAL FROM TREATMENT AND FROM THE STUDY

Subjects may be discontinued from the investigational treatment in the following situations:

- Documented progression of disease or clinical progression
- Death
- Investigator discretion
- Non-compliance with study drug or protocol
- Important protocol deviation
- Pregnancy
- Patient discretion
- Withdrawal of consent (subjects are free to withdraw participation at any time)
- Lost to follow-up
- Subjects incorrectly initiated on study treatment
- Intercurrent illness that would, in the judgment of the investigator, affect assessments of clinical status to a significant degree
- Unacceptable toxicity
- Liver testing abnormalities meeting Hy's Law criteria (See Section 10.4.7)
- Study termination by the Sponsor

Subjects who are withdrawn from the study but are evaluable will not be replaced. Any subject who is withdrawn and is not evaluable may be replaced to ensure a minimum number of evaluable patients.

Subjects may withdraw from any aspect of the voluntary exploratory research at any time, without prejudice to further treatment and independent of any decision concerning participation in other aspects of the study.

If there is strong evidence of clinical benefit and reasons to justify continuation of the study drug, even though treatment discontinuation criteria have been met, this decision must be reviewed with the Sponsor, and continuation of therapy may be allowed assuming all other treatment resumption criteria have been met.

Subjects will be discontinued from the study in the following situations:

- Death
- Lost to follow-up
- Withdrawal of consent
- Study end per protocol
- Early study termination by Sponsor

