8.4.3 TOXICITY MANAGEMENT

Whether or not considered treatment related, all subjects experiencing AEs must be monitored periodically until symptoms subside, any abnormal laboratory values have resolved or returned to baseline levels or they are considered irreversible, or until there is a satisfactory explanation for the changes observed.

In the combination cohorts, in cases where a toxicity cannot be clearly attributed to either drug (ZN-c5 or palbociclib), ZN-c5 should be modified or discontinued first.

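### The combination DLT list (Protocol 8.4.2) omits the Hy's Law item of the monotherapy list (8.4.1), so a Cycle 1 case with only Grade 2 liver values is not a DLT by lab grade and is not counted in the 3+3 rule

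*Protocol*

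**What the plan says.** Protocol 8.4.1 (monotherapy) lists "Liver enzyme and bilirubin abnormalities meeting" Hy's Law criteria as a DLT. It has three further routes that could catch a Grade 2 liver event:

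- an item for Grade 2 or higher events that the investigator judges clinically significant;
- an item for interruptions of 4 days or more due to drug-related toxicity;
- a clause that turns events meeting the stopping criteria into DLTs.

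Protocol 8.4.2 (combination) is a separate list with no reference back to 8.4.1 and none of these items. Outside hematology it has two: "Grade ≥ 3 toxicities despite adequate treatment (e.g., nausea, vomiting, diarrhea", and a palbociclib delay of more than 7 days at the start of Cycle 2. Subjects short of 24/28 ZN-c5 "doses in Cycle 1 for reasons other than DLT will be replaced". Section 6.1.3 repeats the rule, with "at least 18/21 doses of palbociclib in Cycle 1 for reasons other than DLT will be replaced".

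On handling the event itself, 7.2 lists "Liver testing abnormalities meeting" Hy's Law criteria as a reason for discontinuing treatment, with no limit to one study part. When toxicity cannot be attributed to one drug, 8.4.3 says "ZN-c5 should be modified or discontinued first".

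SAP 5.4 determines the MTD in the DLT-Evaluable Analysis Set. The SAP contains no DLT definition that fills the gap.

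**The concern.** The same Cycle 1 liver event is a DLT on ZN-c5 alone and, by lab grade, not a DLT on ZN-c5 plus palbociclib. Palbociclib explains a different hematologic list, but the documents give no reason for dropping the liver item. Protocol 2.3.1 names cholestasis, raised bilirubin and liver cell injury as potential ZN-c5 effects.

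What is at stake is the 3+3 count for the combination. That count sets the combination MTD, and 6.1.3 does not let the RP2D exceed the MTD. An event that leads to stopping ZN-c5 for liver injury could be treated as ordinary under-dosing, and the cohort judged as though it had not occurred.

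**Working it through.** The plan states no figure on this point, so there is none to reproduce. The check has four steps.

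**1. Does a gap exist between the definitions?** Inputs are the thresholds in Protocol 10.4.7 and the grade bands in SAP 11.1.

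| | Hy's Law (10.4.7) | Grade 2 (SAP 11.1) | Overlap |
|---|---|---|---|
| ALT or AST, × ULN | at least 3 | above 3 to 5 | above 3 to 5 |
| Bilirubin, × ULN | above 2 | above 1.5 to 3 | above 2 to 3 |

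Examples, assuming no initial cholestasis and no other cause:

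| ALT, bilirubin (× ULN) | Highest grade | DLT under 8.4.1 | DLT under 8.4.2 by lab grade |
|---|---|---|---|
| 3.1, 2.1 | 2 | yes | no |
| 4, 2.5 | 2 | yes | no |
| 5, 3.0 | 2 | yes | no |
| 5.1, 2.5 | 3 | yes | yes |
| 4, 3.1 | 3 | yes | yes |

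ALT of exactly 3.0 × ULN is Grade 1 and is also missed.

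**2. What happens to the subject?** Post-dose chemistry in Cycle 1 is scheduled on Day 8 (±1) and Day 15 (±2). If ZN-c5 is stopped at the latest permitted day, a once-daily subject has had at most 8 + 1 = 9 or 15 + 2 = 17 doses, both below 24. Under 8.4.2 and 6.1.3 the subject is replaced. SAP 5.4 joins the ZN-c5 and palbociclib dose conditions with and/or. On the *or* reading, a subject who stays on full palbociclib and completes the Day 28 procedures remains evaluable, as a non-DLT. On either route the event is not counted.

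**3. Effect on one cohort (Table 2 of 6.1.3).** With one case uncounted, and no DLT in the replacement if there is one:

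- 1/3 ("Enroll 3 additional subjects in current cohort") becomes 0/3 (escalate);
- 2/6 (do not escalate) becomes 1/6 (escalate).

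**4. Average effect at one dose level.** Let d be the rate of other DLTs and h the rate of Hy's Law cases with no Grade 3 value, mutually exclusive. Both are assumptions, because the documents give neither. The chance of escalating under Table 2 is

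E(p) = (1 − p)³ + 3p(1 − p)⁵,

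with p = d + h if the case is counted, p = d/(1 − h) if uncounted and replaced, and p = d if uncounted and retained. For example, at d = 10% and h = 1%:

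- counted, p = 0.11: 0.7050 + 0.33 × 0.5584 = 0.8892;
- retained, p = 0.10: 0.7290 + 0.30 × 0.5905 = 0.9061.

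| h (d = 10%) | Counted | Replaced | Retained | Gap, replaced | Gap, retained |
|---|---|---|---|---|---|
| 0.5% | 89.78% | 90.53% | 90.61% | 0.8 points | 0.8 points |
| 1% | 88.92% | 90.45% | 90.61% | 1.5 points | 1.7 points |

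For replaced subjects, the gaps at these two rates are 0.5 and 1.0 points at d = 5%, and 0.9 and 1.7 points at d = 20%. With about 40 subjects planned, h of 0.5 to 1% means 40 × 0.005 = 0.2 to 40 × 0.01 = 0.4 expected cases.

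**The case against.** The strongest reply is that the window is narrow and other safeguards surround it. Anything above 5 × ULN for ALT/AST or 3 × ULN for bilirubin is already Grade 3. Combination escalation "will proceed with higher ZN-c5 doses, as tolerated in the Monotherapy Dose Escalation", so each ZN-c5 dose has already passed a list that includes Hy's Law, and the unscreened part is what palbociclib adds. The Safety Review Committee assesses every dose level (10.1.6). The investigator may grade the clinical event as 3, and a long palbociclib delay is itself a DLT. The SAP lists the data, summarizes reasons for exclusion from each analysis set, and summarizes events leading to discontinuation by drug. All of this stands and limits the size. None of it makes the case a DLT, though, and the planned laboratory summaries take each test separately, so no output pairs ALT/AST with bilirubin.

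A second reply is that one added bullet leaves a wider mismatch: in 8.4.2 a Grade 2 liver event that falls short of Hy's Law still leads to replacement if dosing stops. That is true, but it is a separate matter. It is also true that a protocol change now affects no documented ongoing escalation, which is why the fix includes a check of existing data.

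Some stronger readings are not supported:

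- A reader might infer that affected subjects are left on drug. Section 7.2 lists Hy's Law as a discontinuation reason in all parts.
- A reader might infer that the subject always leaves the MTD count. The *or* reading of SAP 5.4 may keep the subject in as a non-DLT.
- A reader might infer that the RP2D is set by this count. The count only caps it.
- A reader might infer a large distortion. At an assumed 5% case rate the same model gives gaps of 8.4 points (replaced) or 9.2 points (retained). Nothing in the documents supports that rate for so narrow a subset, and the model assumes that the Safety Review Committee does nothing.

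**Conclusion.** The point holds as a gap in the formal combination DLT count. A Cycle 1 case with ALT/AST above 3 to 5 × ULN and bilirubin above 2 to 3 × ULN, without initial cholestasis or another cause, is a DLT under 8.4.1 and not, by lab grade, under 8.4.2. No other section closes this.

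The average effect is small: about 0.8 to 1.7 points on the chance of escalating past a dose. That rests on assumed case rates of 0.5 to 1%, 10% other DLTs and no committee action. For a single cohort, however, one uncounted case can decide whether the dose is escalated. The inconsistency is worth correcting because the event is serious and the correction is cheap.

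**What to change.** **Protocol 8.4.2.** Add the Hy's Law item of 8.4.1 with its reference to 10.4.7, and define it for one subject:

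- ALT or AST at least 3 × ULN together with total bilirubin above 2 × ULN, concurrently;
- no initial cholestasis (raised ALP);
- no other explanation.

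Do not require the first component of 10.4.7 as worded there. It compares incidence with a control drug or placebo, which a single subject in an uncontrolled escalation cannot meet. Inclusion criterion 15b admits ALT/AST up to 5 × ULN with liver metastases, so for subjects who enter with such values require a rise from baseline. Once the case is a DLT, the replacement wording needs no change for it.

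**SAP.** Because the 18 May 2022 cut-off has passed, flag every Combination Dose Escalation subject, including replaced ones, who met the ALT/AST and bilirubin thresholds concurrently in Cycle 1. Show baseline values and ALP alongside. After medical review, report whether any combination DLT count would change, labelled as post hoc.

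**Cost.** One bullet and one programmed flag; the analytes are already collected, so no procedure is added. The downside is that a cohort may expand or stop sooner in any further escalation, and a DLT count already used for a dose decision may be questioned.
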